4.5 Multivariable Analysis

Multivariable analysis of the primary objective will be conducted using appropriate regression models (e.g., ordinary least squares [OLS], logistic regression, generalized linear models [GLM], negative binomial regression, Poisson [log-linear] regression) based on the distribution of the measure.

Two multivariable models are planned for the study. Final outcomes for the multivariable analysis will be selected jointly by Optum and GSK after review of descriptive results, including PRO scores, IPTW results, utilization, and costs. Specific predictors to be included in the models will be determined based upon clinical rationale and statistical significance. In general, the statistical significance of each predictor variable will be examined in the univariate regression analysis. Variables that demonstrate at least marginal statistical significance ($p < 0.1$) in univariate analysis will be included in the multivariate models, along with relevant clinical variables regardless of their statistical significance.

Multivariable analyses to assess the primary objective are outlined here. The dependent variable of the first model will be the CAT total score, and the dependent variable of the second model will be the mMRC score. Each model will examine the relationship between symptom burden and treatment (FLUT/SAL or UMEC/VI). Each model will include clinically and analytically meaningful covariates based on the IPTW analysis; it is assumed that the covariates will be the same for each model.

Depending on the distribution of the measure, the CAT and mMRC outcomes may be analyzed as a continuous or dichotomous measure. In general, continuous variables are analyzed using ordinary least square regression models. If transformed into a dichotomous measure (e.g., patients with a CAT total score > 10 or an mMRC score ≥ 2), the probability of an event will be modeled using logistic regression. Logistic regression models fit a maximum-likelihood logit model. Following standard procedure, regression diagnostics will be performed for each model to assess goodness of fit and violations of model assumptions (e.g., multicollinearity, heteroskedasticity). When there are violations of the model, they will be noted and appropriate corrections made to the data (i.e., typically through transformation of either the independent or dependent variables) or in the method of estimation. In addition, the fitted and the observed data will be examined to uncover outliers, their effect on the analysis, and possible misspecification of the initial equation.

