Data Analysis Methods	
Study endpoints and all other study variables will be analyzed descriptively. Numbers and percents will be provided for dichotomous and polychotomous variables. Means, medians, and standard deviations will be provided for continuous variables. Means and standard deviations will be provided for cost and utilization measures.
 
Primary Endpoints
 
Patient-reported symptom burden. Scores will be presented from validated instruments measuring dyspnea (mMRC) and condition-related burden of illness (CAT). Mean total, summary, and/or domain scores and standard deviations will be presented for each scale/item). Results will be presented for the overall study sample and will compare self-reported FLUT/SAL to UMEC/VI treatment cohorts. To address the objective of comparing symptom burden of patients by treatment cohort (FLUT/SAL as compared to UMEC/VI), inverse probability of treatment weighting (IPTW) will be applied to reduce confounding on observed clinical, demographic, and sociodemographic characteristics.
 
Proportion of patients reporting COPD symptoms while treated with FLUT/SAL or UMEC/VI. The proportion of patients who report COPD symptoms will be calculated as the number of COPD patients who report COPD symptoms as measured by the CAT, divided by the total number of respondents. Results will be presented for the overall study sample and by treatment cohort (FLUT/SAL or UMEC/VI).
 
Secondary Endpoints
 
Baseline health care resource utilization and costs. All-cause and COPD-related health care costs will be presented for the 12-month baseline period. Mean, median, and standard deviations will be presented for total costs and utilization and by each category of costs. Costs and counts will be presented overall and for the subset of patients utilizing the selected type of service. The proportion of patients receiving services for each type of service and the proportion of patients with non-zero costs for each type of cost will be calculated. Results will be presented for the overall study sample and by treatment cohort (FLUT/SAL or UMEC/VI).
 
Patient clinical characteristics. The proportion of patients with evidence of selected clinical characteristics will be presented. The top 20 claims-based comorbidities and 10 COPD-related comorbidities of interest will be identified. The percent of patients with each condition will be identified. Mean and standard deviation will be calculated for the Quan-Charlson comorbidity score. Results will be presented for the overall study sample and may be stratified by relevant subgroups for analysis (e.g., by symptom severity as measured by the mMRC and CAT, and by treatment).
 
Patient GOLD classification. The proportion of patients in each GOLD category of symptom burden and exacerbation (A, B, C, D) will be identified using the baseline

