
	
count of COPD exacerbations combined with CAT total score and mMRC score. GOLD categories are mutually exclusive. Results will be presented overall and by treatment cohort (FLUT/SAL or UMEC/VI).
 
Multivariable modeling of the primary objective will be conducted following review of descriptive and IPTW results. Each model will examine the relationship between symptom burden and treatment with FLUT/SAL or UMEC/VI. The dependent variable for the models will be CAT total score and mMRC score, respectively; covariates for the models will be based on clinical and analytic significance.

Sample Size and Power
	
The study sample is estimated to include 385 patients per cohort with evidence of COPD diagnosis and single-inhaler dual therapy treatment with FLUT/SAL or UMEC/VI. A sample size of n=385 per cohort is required to assess statistical significance with a 95% confidence interval at ± 0.05 with 80% power. A sampling frame of 2,700 patients is estimated to be used to reach the target evaluable sample size, n=770 patients (385/cohort). Based on patient counts and response rate estimates, it is anticipated that two waves of data collection will be needed to meet the target sample size.
 
This estimated study sample size is sufficient to detect proportional differences in PRO outcomes between two cohorts of patients (i.e., patients treated with FLUT/SAL or UMEC/VI who have severe symptoms as measured by a CAT total score ≥ 10 or an mMRC score ≥ 2); other stratifications tied to primary and secondary endpoints may be considered for statistically powered analyses as sample size allows.

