3.4 Endpoints

Patient-reported outcomes, which include all primary endpoints, will be measured using the cross-sectional survey at the time of survey administration. Claims-based characteristics, including economic endpoints, will be measured in the baseline period, which is the 12-month period prior to survey sample identification.

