3.4.1 Primary Endpoint

- **Patient-reported symptom burden.** Scores will be presented from validated instruments measuring dyspnea (mMRC) and condition-related burden of illness (CAT). Mean total, summary, and/or domain scores and standard deviations will be presented for each scale/item (as described in Section 3.3.1.3). The proportion of patients with high and low symptom burden on both PRO measures will be calculated. Results will be presented for the overall study sample and by treatment cohort (FLUT/SAL or UMEC/VI).
- **Proportion of patients reporting COPD symptoms while treated with FLUT/SAL or UMEC/VI.** The proportion of patients who report COPD symptoms will be computed for survey respondents. Two calculations will be presented: the number of COPD patients who report COPD symptoms as measured by a CAT total score ≥ 10 , divided by the total number of respondents with a CAT total score; and the number of COPD patients with an mMRC score of 2-4, divided by the total number of respondents with an mMRC score. Results will be presented for the overall study sample and by treatment cohort.
- The mMRC and CAT instruments are included to correspond with current GOLD guidelines.

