3.5 Sample Size / Power Calculations

The sample size required for the study is based on several requirements. First, the study's primary outcome measures will be proportions (e.g., the proportion of patients experiencing symptoms who report low versus high symptom severity as measured by the mMRC and CAT total score). The estimated sample size is determined by the value and desired precision of the measured proportions.

Figure 6 displays the sample sizes required for various proportions, assuming a 95% confidence interval and a precision of ± 0.05 . Because the actual population proportions (e.g., the proportion of patients in each treatment cohort with mMRC scores ≥ 2 and the proportion of patients in each treatment cohort with CAT total scores ≥ 10) are unknown, the largest sample size indicated with that precision was selected. This largest value is for a proportion of 0.5 and assures a 95% confidence interval of ± 0.05 or

better for all proportions observed. Thus, a sample size of 385 completed patient surveys per treatment cohort was selected.

Figure 6 – Sample Sizes Required for Various Proportions

95% Confidence Interval	Proportion								
	0.9	0.8	0.7	0.6	0.5	0.4	0.3	0.2	0.1
±0.05	139	246	323	369	385	369	323	246	139

Since the proportion of patients experiencing symptoms will be determined from the survey and a variety of exclusion criteria can be applied only after data collection, a sampling frame of 2,700 patients is needed for an estimated evaluable sample size of 385 patients per treatment cohort. The sampling frame will be comprised of equal proportions per medication cohort (n=1,350 per cohort); however, proportional response rate by treatment cohort cannot be guaranteed. Based on the feasibility counts, Optum estimates that two waves of sample identification and survey data collection will be required to meet the target sample size. Sample identification for wave 2 will occur as soon as sufficient sample is available, which is estimated to be the month following wave 1 sample identification. The availability of the second wave will be assessed during protocol development.

Figure 7 – Estimated Final Evaluable Sample Size

Sampling frame per treatment cohort	n=1,350
Estimated response rate (30-35%)	405-470
Exclusion criteria applied following claims lag (2-5% ineligible)	8-24
Estimated final evaluable sample size per treatment cohort	385-446
Estimated total final evaluable sample size	770-892

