3.6 Hypotheses

The primary objective is to assess patient-reported COPD symptom burden among patients treated with UMEC/VI as compared to FLUT/SAL. The hypothesis for the primary objective is:

Null hypothesis:

- 1A) Patient-reported symptom severity as measured by CAT total score will not differ for UMEC/VI patients as compared to FLUT/SAL patients.
- 1B) Patient-reported symptom severity as measured by mMRC score will not differ for UMEC/VI patients as compared to FLUT/SAL patients.

Alternative hypothesis:

- 1A) Patient-reported symptom severity as measured by CAT total score will differ for UMEC/VI patients as compared to FLUT/SAL patients.
- 1B) Patient-reported symptom severity as measured by mMRC score will differ for UMEC/VI patients as compared to FLUT/SAL patients.

Hypotheses are presented for the primary objective since the sample size / power calculations are based on assessment of the primary objective.

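### Section 4.5 lets the outcomes of the primary-objective models be selected after PRO scores have been reviewed, although CAT and mMRC are already named; the CAT cut-off is inconsistent and the modelled form is left open

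*Combined protocol and SAP*

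**What the plan says.** **Outcome of the models.** Section 4.5 plans two multivariable models and then says: "Final outcomes for the multivariable analysis will be selected jointly by Optum and GSK after review of descriptive results, including PRO scores, IPTW results". The same sentence adds utilization and costs to the material reviewed. The next paragraph of 4.5 gives CAT total score as the outcome of the first model and mMRC score as that of the second. The synopsis agrees: "The dependent variable for the models will be CAT total score and mMRC score, respectively". Hypotheses 1A and 1B in 3.6 concern the same two measures, for example: "1A) Patient-reported symptom severity as measured by CAT total score will not differ for UMEC/VI patients as compared to FLUT/SAL patients". Section 4.1 and the first sentence of 4.5 confine the modelling to the primary outcome and the primary objective.

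**What is seen first.** On patient-reported symptom burden the synopsis says: "Results will be presented for the overall study sample and will compare self-reported FLUT/SAL to UMEC/VI treatment cohorts". Section 3.4.1 also presents these results by cohort.

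**Form of the outcome.** Section 3.5 bases the sample size on the statement that the study's "primary outcome measures will be proportions". Section 3.4.1 reports mean scores and also says: "The proportion of patients with high and low symptom burden on both PRO measures will be calculated". Section 4.5 allows CAT and mMRC to be modelled as continuous or dichotomous according to their distribution.

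**CAT cut-off.** Section 3.4.1 counts patients with "COPD symptoms as measured by a CAT total score ≥ 10", and the synopsis and 3.5 use the same threshold. Section 4.3 (under Primary Objective) and the example for the logistic model in 4.5 use >10. The mMRC cut-off is 2 or more throughout.

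**The concern.** A sentence that defers the choice of model outcome until results have been reviewed cannot stand beside text that has already made the choice. If it were followed, the outcome of an adjusted model for the primary objective could be picked with the cohort difference in view. That holds even if the IPTW results in the review are only balance diagnostics, because the PRO scores themselves are shown by cohort.

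The adjusted analysis carries weight here. The cohorts are a non-random convenience sample (3.2.2), and the protocol relies on weighting and modelling to deal with confounding.

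Even if CAT and mMRC are kept, the form of each modelled outcome and the CAT threshold are not settled. Both can change whether a given data set shows a difference.

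**Working it through.** **1. The passages side by side**

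| Question | Text that settles it | Text that reopens or contradicts it |
|---|---|---|
| Which outcomes are modelled? | Synopsis, 3.6 and 4.5 (next paragraph): CAT total score and mMRC score | 4.5: selected after review of PRO scores, IPTW results, utilization and costs |
| Which form? | 3.5: proportions | 4.5: score or dichotomy, by distribution, no criterion; 3.4.1 reports both |
| Which CAT cut-off? | Synopsis, 3.4.1, 3.5: ≥10 | 4.3, 4.5: >10 |

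The first and third rows are contradictions. The second is mainly an open specification: 1A and 1B refer to severity as measured by the score and do not say whether a mean or a proportion is compared. The tension is between 3.5, which says proportions, and 4.5, which allows either.

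**2. The plan's own figure**

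Section 3.5 gives 385 per cohort. n = 1.96² × 0.5 × 0.5 / 0.05² = 384.2, rounded up to 385. It reproduces, as a precision figure for a single proportion. It does not depend on which form is modelled, and nothing below changes it.

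**3. Patients affected by the cut-off**

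Only patients scoring exactly 10 change group. The documents give no CAT mean or SD, so both are assumed. With an approximately normal score, P(CAT = 10) = Φ((10.5 − mean)/SD) − Φ((9.5 − mean)/SD).

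- Mean 12, SD 7: 0.0547, and 0.0547 × 770 = 42 patients.
- Mean 20, SD 7: 0.0206, and 0.0206 × 770 = 16 patients.

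These are the extremes over means of 12-20 and SDs of 7-9.

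**4. Score against proportion**

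This is a simulation for illustration: 385 per cohort, unweighted two-sided tests at 0.05, CAT as a rounded normal limited to 0-40, assumed SD 8 and mean 14 or 18. A shift of 0.2 SD is then 0.2 × 8 = 1.6 CAT points. The table shows how often the mean score and CAT ≥10 disagree on p<0.05. Ranges cover both means and, at 0.2 and 0.4 SD, both directions of shift.

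| True shift | Studies in which the forms disagree |
|---|---|
| None | 6-7% |
| 0.1 SD | 19-23% |
| 0.2 SD | 26-43% |
| 0.4 SD | 1-10% |

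Disagreement is near its highest at 0.2 SD. There, power is about 79% for the mean, and in one set of runs 55% (mean 14) or 44% (mean 18) for CAT ≥10. The proportion is significant while the mean is not in only about 2-3% of studies. Most of the disagreement is therefore power lost by dichotomising.

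**The case against.** The case for leaving the text alone has several parts, and much of it stands.

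- **CAT and mMRC are named, so the sentence does no harm.** In part. Because the synopsis, 3.6 and 4.5 name the outcomes, a report that modelled something else would visibly depart from the protocol. A reader might infer that a switch of outcome could not be detected; the documents do not support that. Section 4.1 and the opening of 4.5 also count against using utilization or cost as an outcome of these models. But the sentence still states the opposite rule, and the protocol does not say which text governs.
- **A weighted comparison of CAT and mMRC would exist anyway.** Possibly. A reader might infer that a substituted outcome would push CAT or mMRC out of the adjusted analysis altogether. That is not established. The synopsis and 4.4 can be read as giving an IPTW comparison of symptom burden whatever is modelled later, although 4.4 also ties the weights to the multivariable model.
- **Both forms are reported.** This stands for the descriptive results in 3.4.1. What remains open is the form used in the adjusted model.
- **Form depends on distribution, not effect.** True as written. But 4.5 gives no criterion, does not say that cohorts are pooled for the decision, and places modelling after the descriptive review.
- **The SAP or the table shells will settle it.** Section 4.1 defers specific tests to table shells, and 3.1.5, 3.3.2, 4.2 and Appendix 2 defer dates, definitions and scoring to a SAP. None says that the model outcome or its form will be locked before cohort results are seen.
- **The cut-off is editorial.** Taken alone it is minor, and the value in 4.5 is only an example. It nevertheless separates the primary endpoint definition in 3.4.1 from the primary-objective classification in 4.3.

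**Conclusion.** The point holds, as one to correct before cohort results are reviewed. The outcome-selection sentence in 4.5 is wrong as written, because it contradicts the named outcomes and places the choice after PRO scores are available by cohort. The CAT cut-off is inconsistent between sections. The modelled form is under-specified rather than contradictory within 4.5, and it could be settled after the cohort results are known.

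The cut-off affects an estimated 2-5.5% of patients, and that range rests on the assumed CAT distribution. The disagreement percentages rest on the same kind of assumption and on unweighted tests, whereas the plan's analysis is weighted or adjusted. A reader might take them as the error inflation caused by the selection sentence. They are not: the protocol states no selection rule, so that inflation cannot be computed, and no direction of bias is implied. They show only that form is not a neutral choice. The sample size of 385 per cohort is not affected.

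**What to change.** 1. In 4.5, delete the sentence that selects outcomes after review, or limit it to additional exploratory models labelled as such.
2. State in 4.5 and in the SAP that CAT and mMRC are the outcomes of the two models. Give each one primary form, fixed before any outcome is compared by cohort, and keep the other form as a sensitivity analysis. If the distribution is to decide, write down the criterion and apply it with the cohorts pooled.
3. Use one CAT cut-off in the synopsis, 3.4.1, 3.5, 4.3 and 4.5. Which form and which cut-off to use is the sponsor's choice.
4. Bring the statement in 3.5 about proportions into line with the chosen primary form. If a score is made primary, 3.5 would also need an SD and a target difference, which the documents do not give.

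The cost is protocol and SAP text; no new data are needed. The sponsor and vendor give up the freedom to change outcome or form after seeing results.

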11 APPENDIX 4. COVARIATES OF INTEREST FOR IPTW

The following is a list of covariates planned for inclusion in the IPTW analysis. Final covariates included in the multivariable models will be determined following review of the comparison of weighted and non-weighted descriptive results as described in Sections 4.3 - 4.4.

Clinical characteristics

- General health
- BMI
- Current smoking status
- Pack years
- Years since COPD diagnosis
- Baseline Quan-Charlson comorbidity score
- Count of COPD-related comorbid conditions
- Count of all-cause baseline medication fills
- Count of COPD-related baseline medication fills
- Count of all-cause baseline ambulatory visits (office and/or outpatient)
- Count of COPD-related baseline ambulatory visits (office and/or outpatient)
- Count of baseline COPD exacerbations

Demographic and sociodemographic characteristics

- Age
- Sex
- Race
- Ethnicity
- Geographic region
- Population density
- Marital status
- Household income
- Education

ⁱ Dillman DA. Mail and Internet surveys: the tailored design method, second edition. New York: John Wiley & Sons, Inc.

ⁱⁱ Edwards P, Roberts I, Clarke M, et al. Increasing response rates to postal questionnaires: systematic review. *BMJ*. 2002;324:1183.

ⁱⁱⁱ Following the Dillman tailored design method, Optum's standard data collection time period is 8 weeks.

^{iv} Doherty, DE, Belfer, MH, Brunton, SA, Fromer, L, Morris, CM, Snader, TC. Chronic Obstructive Pulmonary Disease: Consensus Recommendations for Early Diagnosis and Treatment. *J Fam Prac*, 2006.

^v Bestall C, Paul EA, Garrod R, et al. Usefulness of the Medical Research Council (MRC) dyspnea scale as a measure of disability in patients with COPD disease. *Thorax* 1999;54:581-586.

^{vi} Jones PW, et al. Development and first validation of the COPD Assessment Test (CAT). *Eur Respir J* 2009;34(3):648-654.

^{vii} Jones PE, et al. Properties of the COPD Assessment Test (CAT) in a cross-sectional European study. *Eur Respir J* 2012; doi: 10.1183/09021936.00177210.

^{viii} Quan H, Li B, Couris CM, Fushimi K, Graham P, Hider P, Januel JM, Sundararajan V. Updating and validating the Charlson comorbidity index and score for risk adjustment in hospital discharge abstracts using data from 6 countries. *Am J Epidemiol*. 2011;173(6):676-82.

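### Section 4.5 and Appendix 4 give unreconciled rules for choosing covariates in the two primary outcome models, one of them a univariate p<0.1 screen; one shared list should be fixed in advance

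*Combined protocol and SAP*

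**What the plan says.** Three bases for choosing covariates appear in the current text.

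- **Screen plus clinical judgement (Section 4.5, second paragraph).** The screen is introduced as the general approach: "the statistical significance of each predictor variable will be examined in the univariate regression analysis". "Variables that demonstrate at least marginal statistical significance", set at p<0.1, go into the multivariable models, "along with relevant clinical variables regardless of their statistical significance". No clinical variable is named.
- **IPTW-based, shared set (Section 4.5, third paragraph).** "Each model will include clinically and analytically meaningful covariates based on the IPTW analysis", and "it is assumed that the covariates will be the same for each model".
- **After review (Appendix 4).** "Final covariates included in the multivariable models will be determined following review of the comparison of weighted and non-weighted descriptive results".

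The synopsis adds only that covariates rest on clinical and analytic significance and that modelling follows review of the descriptive and IPTW results.

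Section 4.4 bears directly on the consequences. The propensity model uses predetermined covariates (Appendix 4 lists 21: 12 clinical, 9 demographic or sociodemographic), and the resulting weights are to be applied in the corresponding multivariable model. The p<0.1 screen does not govern the propensity model. Section 4.5, which specifies the CAT and mMRC models, does not mention the weights.

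**The concern.** These two models give the adjusted treatment comparison for the primary objective. Two analysts following the text faithfully could fit different models, because nothing says which basis prevails or how the three combine.

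The screen is the weakest of the three. A confounder is related to both treatment and outcome, but a univariate outcome p-value looks only at the outcome. A weak but real confounder can fail it by chance, and a variable with no relation to the outcome passes one time in ten. The interval from the final model takes no account of the selection. Run once for CAT and once for mMRC, the screen will tend to return two sets, which fits poorly with the assumption of a common one.

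Timing is the other issue. The screen uses the outcomes by construction. A review confined to covariate balance would not, but Appendix 4 points to Section 4.3 as well as 4.4, and Section 4.3 includes the outcome comparisons. The adjustment set for the primary estimate can therefore be settled after CAT and mMRC scores have been seen.

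**Working it through.** **Inputs from the plan.** 385 patients per cohort, 770 in total (Section 3.5); 21 covariates (Appendix 4); entry at p<0.1 (Section 4.5). The plan gives no figure for the screen itself. Its sample size reproduces: 1.96² × 0.5 × 0.5 / 0.05² = 384.15, rounded up to 385.

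**Assumed inputs.** The documents give no covariate effects, no cohort differences and no CAT–mMRC correlation. All such values below are assumptions, shown as ranges where possible.

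**1. Chance that a real covariate fails the screen.** With correlation r to the outcome, m = atanh(r) × √(N − 3) and P(fail) = Φ(1.645 − m) − Φ(−1.645 − m). For N = 770 and r = 0.05, m = 0.05004 × 27.69 = 1.386, so P(fail) = Φ(0.259) − Φ(−3.03) = 0.60.

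| r | P(fail), N = 770 |
|---|---|
| 0.03 | 0.785 |
| 0.05 | 0.60 |
| 0.07 | 0.38 |
| 0.10 | 0.13 |
| 0.15 | 0.006 |

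The loss is large for weak predictors and negligible for strong ones. If all 21 were pure noise, 21 × 0.1 = 2.1 would be expected to pass.

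**2. Agreement between the CAT and mMRC screens.** Take equal r for both outcomes and a correlation of 0.4 to 0.8 between the two screening statistics. The chance d that the screens disagree on one covariate is 10–16% at r = 0, 20–36% at r = 0.05, 10–18% at r = 0.10 and about 1% at r = 0.15. Treating the 21 as independent, P(at least one disagreement) = 1 − (1 − d)^21. At d = 0.10 this is 1 − 0.9^21 = 0.89; at d = 0.20 it is 0.99; at d = 0.01 it is 0.19. In a joint simulation of the setting in step 3, with a residual CAT–mMRC correlation of 0.6, the two sets differed in more than 99% of runs, by about 6 covariates.

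**3. Bias, outcome model unweighted.** The simulation has 770 patients, 21 independent covariates each differing by 0.15 SD between cohorts, each shifting CAT by 0.05 SD in the same direction, CAT SD 8, and no drug effect. Crude confounding is 21 × 0.15 × (0.05 × 8) = 1.26 points. Over repeat simulations of this setting:

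- The screen kept 9.4 to 9.7 of 21 covariates, left a bias of 0.32 to 0.35 points and rejected the true null 8.0 to 8.8% of the time.
- The full fixed set gave a bias of 0.01 points and rejection of 4.6 to 5.1%.

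As a cross-check, a bias of 0.34 on an SE of 0.574 is a shift of 0.59 SE, and Φ(−1.37) + Φ(−2.55) = 0.085 + 0.005 = 0.09, in line with the simulated rate.

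**4. Bias, outcome model weighted as in Section 4.4.** In the same setting, with weights from a correct propensity model on all 21 covariates, weights plus screen gave a bias between −0.04 and 0.01 points and rejection of 4.8 to 6.0%. In the run with 6.0%, weights plus the full set gave 0.01 points and 6.4%, so the screen is not the source. Simulation error on a 5% rate with 1,500 runs is √(0.05 × 0.95 / 1500) = 0.6 percentage points.

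**5. Sensitivity.**

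- Drawing treatment from a logistic model (log-odds 0.12 per SD for each covariate), with outcome effects of 0.03, 0.05 or 0.08 per SD, the unweighted screen left 0.035 to 0.039 SD, or 0.28 to 0.31 points at SD 8, with rejection of 7.4 to 7.9%. With weights, bias was within 0.002 SD and rejection was 4.4 to 5.9%.
- If the covariates' directions cancel, the unweighted screen shows no bias and 4.9% rejection.
- If the clinical-variables clause is taken to retain all 12 clinical items in Appendix 4 (an assumption), the unweighted bias falls to 0.16 points and rejection to 4.5%.

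**The case against.** The strongest reply is that the main control of confounding is never screened. Section 4.4 builds the weights on predetermined covariates and puts them in the outcome model, so a variable lost to the screen is still balanced. Section 4.5 also keeps relevant clinical variables whatever their p-value, introduces the screen only as the general approach, and merely assumes a common covariate set.

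Most of this stands, and it rules out two stronger readings that a reader might infer:

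- *That the planned analysis loses real confounders and carries a bias of about 0.3 points with about 8% false rejection.* The documents do not support this. Those figures belong to an unweighted model, and Section 4.4 plans a weighted one.
- *That the plan contradicts itself on the shared set.* It does not strictly do so. Using the union of the two screens plus the clinical variables would satisfy both sentences. The plan states no such rule, so the passages are unreconciled rather than contradictory.

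Three things remain. Section 4.5 never repeats the weighting, so an unweighted fit is a possible reading of it. If the propensity model proves inadequate, the outcome-model covariates are the backstop, and the screen thins them. Good weights also do nothing about a covariate list settled after results are known.

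A separate caution concerns the remedy. Forcing every Appendix 4 item into the models is not automatically safe. General health is a survey item recorded alongside CAT and mMRC (Section 3.3.1.1). Fills and exacerbations are counted over 12 months, although Section 3.2.1.1 places the start of study drug in the last six of them. Adjusting for what happens on treatment could remove part of the difference under study.

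**Conclusion.** The concern holds as a problem of prespecification, and the text alone shows it: three bases for one adjustment set, unnamed clinical variables, and a choice that can follow sight of the outcomes. Different covariate sets for CAT and mMRC are very likely if many predictors are weak (89% or more for r up to 0.10, assuming independence), and much less so if all are strong.

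The numerical consequence is conditional. With the Section 4.4 weights applied and an adequate propensity model, the screen adds essentially no bias. Without them, the roughly 0.3-point bias and 8% rejection rate rest on assumed effect sizes and on all confounders acting in one direction, which is the unfavourable case. No sample-size figure in the plan depends on this point. It merits a change because the change is simple and concerns the primary comparison, not because the planned weighted estimate has been shown to be biased.

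**What to change.** Delete the univariate p<0.1 screen from Section 4.5 and the after-review clause from Appendix 4. In both places, state along these lines:

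> The CAT and mMRC outcome models are both IPTW-weighted. Each includes treatment and the same list of covariates, drawn from Appendix 4 and fixed before survey outcomes are seen. No covariate is added or dropped on the basis of a p-value.

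Before fixing the list, decide and record whether items measured on treatment belong in it: general health, and fills or exacerbations after drug start. The same decision should be carried through to the propensity model, since the weights adjust for whatever that model contains.

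The cost is wording plus a little precision. Unweighted, the full set raised the spread of the estimate by about 4% in one simulation (0.596 v 0.574) and 5% in another (0.617 v 0.586). Weighted, no loss was visible (0.629 v 0.630). These simulations gave each covariate one parameter. If coding the categorical items brought the total to about 40 (an assumption), the unweighted loss would grow by roughly √(749/730) − 1 = 1%.
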